Type 1 Diabetes and Life (T1DAL) Measures: Separate versions of this quality of life questionnaire³⁰³⁻³⁰⁴ have been developed for 8-11 year olds with T1D (36 items), 12-17 year olds with T1D (44 items), parents of 8-11 year olds with T1D (47 items) and parents of 11-17 year olds with T1D (50 items). Empirically derived condensed versions of these instruments are undergoing validation.

Problem Areas in Diabetes Scale (PAID): (Teen and Parent brief versions). Respondents rate their agreement with 14 (Teen) or 15 (Parent) statements related to their worry and burden about their diabetes.³⁰⁶⁻³⁰⁸ Items are rated on a 6-point scale from "not at all" to "serious problem", and higher scores reflect less perceived burden/worry. Wasserman et al.³⁰⁹ recently validated the condensed versions of both scales.

Diabetes-Specific Risk-Taking Inventory (DSRI): The DSRI is a 34-item adolescent report measure that assesses the frequency with which adolescents (ages 15-18) engage in diabetes-specific risk-taking behaviors.³¹⁰ Adolescents report the frequency of each behavior on a 5 point likert scale, with the options of "Daily (5), Weekly (4), Monthly (3), Every few months (2), Yearly (1), Never (0), and Not Applicable." A mean score is used, with a higher score indicating more frequent diabetes-specific risk-taking behavior. In a validation study with 224 adolescents, the DSRI demonstrated excellent internal reliability ($\alpha = .90$).

Family-Centered Care Assessment (FCCA): The FCCA³¹¹ is a consumer-driven measure of the degree to which medical care received for a specific medical condition achieves ten accepted principles of family centered care. There are parallel, validated, 24-item forms for completion by parents and adolescents.

Collaborative Parent Involvement Scale (CPI): The 12-item CPI obtains youths' level of teamwork in T1D care with a specified adult.¹⁵⁷ Those living with two parents will complete the CPI separately about each. Higher total scores indicate that the youth perceives more T1D collaboration with that caregiver. Cronbach's α was .93 and .96 for youths' ratings of primary and secondary caregivers, respectively.

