
Sample Size and Statistical Power: Recruitment ended at the end of March 2020. A total of 115 families were recruited. Allowing for some attrition prior to randomization, a sample of 100 patients (65 TC and 35 UC) yields 87.4% power to detect a clinically meaningful group differences in mean HbA_{1c} of 0.5% (~0.7 SD) versus the alternative of equal means using a t test with $p = .05$. Limiting recruitment to those with HbA_{1c} = 7.5-10.0% is anticipated to reduce the SD from 1.5% for the general adolescent T1D population to 0.7%, boosting effective statistical power for the RCT. The predicted 12-month means are 8.1% (TC) and 8.6% (UC). If the SD is 1.0%, our power is reduced to 71.3%; if it is 1.5% as in the general population, our power is 50.9%. This sample size also achieves power of 78.2% to detect a clinically meaningful mean differences in the DSMP-SR

total score of 7.0 points (~0.6 SD) at 1 year. The estimated mean values are 63.0 (TC) and 56.0 (UC). This preliminary trial will yield rich data that could be used to guide the sampling plan for a future, more ambitious, multi-center trial.³²⁵⁻³²⁷ The following hypotheses will be tested:

Hypothesis 1: Compared with UC patients, those randomized to TC will have significantly more favorable primary (HbA_{1c} and DSMP-SR scores) and secondary (frequency of severe hypoglycemia and level of glycemic variability) diabetes management outcomes at their 6, 9, and 12 month follow-up visits.

Hypothesis 2: Compared with UC patients, those randomized to TC will demonstrate more favorable scores on the T1DAL, PAID, and CPI at follow-up measurements.

Hypothesis 3: Significantly higher scores will be obtained on the DCI completed by HCPs describing TC care compared to HCPs describing UC care.

Hypothesis 4: Effects of TC on HbA_{1c} and DSMP-SR scores will be moderated by demographic variables (youth age, family SES, # of adult caregivers in the home) and by baseline scores on the T1DAL, PAID, and CPI. More benefit from TC will accrue to youth who are younger, from two-parent families with higher SES, and with more favorable scores on the T1DAL, PAID and CPI.

Hypothesis 5: Effects of TC on HbA_{1c} and DSMP-SR scores will be mediated by changes in scores on the T1DAL, PAID, and CPI. More benefit from TC will accrue to youth with favorable changes in T1DAL, PAID and CPI scores during the 12 months of the study.

[figure not shown]

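### The stated PAID score direction runs opposite to its printed response anchors with no reverse-scoring described, so a fall in distress under TC could be reported as a worsening

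*Combined protocol and SAP*

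**What the plan says.** The measure is described in section 3.4 (Approach, Part 2), in the entry for the Problem Areas in Diabetes Scale. It says: "Respondents rate their agreement with 14 (Teen) or 15 (Parent) statements related to their worry and burden about their diabetes". The end-points of the six-point item scale are *not at all* and *serious problem*. The sentence giving those anchors continues: "and higher scores reflect less perceived burden/worry". The entry gives no numeric item codes, no total or mean formula and no reverse-scoring step.

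The DSRI entry that follows lists a number for each response option and then a direction that agrees with those numbers: "A mean score is used, with a higher score indicating more frequent diabetes-specific risk-taking behavior".

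PAID is used in three hypotheses, none of which states a numeric direction:

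- Hypothesis 2 predicts that TC patients "will demonstrate more favorable scores on the T1DAL, PAID, and CPI at follow-up measurements".
- Hypothesis 4 takes baseline PAID as a moderator and predicts more benefit for youth "with more favorable scores on the T1DAL, PAID and CPI".
- Hypothesis 5 takes change in PAID as a mediator and speaks of favorable changes.

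Analytic Plans adds no PAID direction. Table 3 schedules PAID for adolescents and parents at 0, 6 and 12 months. Specific Aim 2 lists T1D-related distress among the TC-UC comparisons.

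**The concern.** The items are about worry and burden, and the upper anchor is a serious problem. A score built from ratings in the printed order therefore goes up as burden goes up, yet the plan says that it goes down. This is a scoring rule that is stated and that conflicts with the response scale in the same sentence. It is more than a detail left out.

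No other supplied text tells an analyst which PAID direction is favorable. An analyst who codes the ratings as printed and labels results by the written rule would follow the protocol and still put the wrong label on the result. The p-value would give no warning, because most tests are two-sided: a significant benefit would appear as a significant deficit. Distress is a named comparison in Aim 2, and the trial is meant to inform a larger one, so a reversed label could be carried forward.

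**Working it through.** The plan gives no PAID figure to reproduce. The check compares the two statements and then follows a reversal through each hypothesis.

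**1. Direction implied by the anchors.** The documents give 14 items (Teen) and 15 items (Parent) with six response points. Item values are not given, so 0-5 and 1-6 are both assumed. Total = number of items × item value.

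| Form | Assumed coding | All *not at all* | All *serious problem* |
|---|---|---|---|
| Teen | 0-5 | 14 × 0 = 0 | 14 × 5 = 70 |
| Teen | 1-6 | 14 × 1 = 14 | 14 × 6 = 84 |
| Parent | 0-5 | 15 × 0 = 0 | 15 × 5 = 75 |
| Parent | 1-6 | 15 × 1 = 15 | 15 × 6 = 90 |

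In every row the higher score means more burden, against the written direction. A mean in place of a sum changes nothing here. Only reversed items give the written direction.

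**2. Effect of a reversal.** Let x be the anchor-order score and x′ = C − x the reversed score. For 14 items coded 1-6, each item becomes 7 − r, so C = 14 × 7 = 98. A change from baseline d becomes d′ = −d.

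- *Hypothesis 2:* the TC-UC difference changes sign. Its standard error and two-sided p-value do not.
- *Hypothesis 4:* the treatment × baseline PAID coefficient changes sign, with the same p-value.
- *Hypothesis 5:* path a (treatment to PAID change) becomes −a, and path b (PAID change to outcome) becomes −b. The indirect effect is (−a)(−b) = ab, unchanged.

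**3. Numerical illustration.** One simulated data set was analysed under both codings. Group sizes of 65 TC and 35 UC come from the Sample Size paragraph. Everything else is assumed: baseline PAID mean 45 and SD 12, a 6-point fall under TC, residual SD 8, and an HbA1c-like outcome with residual SD 0.7.

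| Quantity | Anchor order | Reversed | Two-sided p |
|---|---|---|---|
| H2: TC-UC difference in PAID change | −6.95 | +6.95 | 7.3 × 10⁻⁵ for both |
| H4: interaction with baseline PAID | −0.0026 | +0.0026 | 0.85 for both |
| H5: path a | −6.954 | +6.954 | not computed |
| H5: path b | +0.0194 | −0.0194 | not computed |
| H5: indirect effect ab | −0.1348 | −0.1348 | not computed |

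The product ab was taken before rounding the paths. The magnitudes carry no information about this trial; only the signs matter.

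**4. Reading the anchor-order column by the written rule.** The −6.95 is a real fall in burden under TC. The rule equates a lower score with more burden, so the result would be reported as TC worse by 6.95 points. In Hypothesis 4, a high-distress baseline group would be described as the low-distress one, so a result against the prediction could be reported as supporting it, or the reverse. In Hypothesis 5, a falling score would be called an unfavorable change, although the size and sign of the mediated effect are right.

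**The case against.** The strongest reply is that the conflict is inferred. The anchors describe item ratings, while the direction clause describes scores. If items are reverse-scored before they are combined, both statements are true and only a scoring step is unwritten. The questionnaires are listed in the Appendix but not reproduced, and the entry cites validation sources, so a key may settle the matter. This stands as far as it goes: the supplied text cannot show which statement is wrong, or whether either is. It does not remove the need for a correction, because the protocol's own sentence has to agree with the key, and at present it does so only through a step nobody has written down.

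It is also fair to say that PAID is a secondary questionnaire and that two-sided tests do not change. Both are accepted.

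A reader might infer more than the documents support:

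- *That the misreading will happen.* It needs anchor-order coding and the written rule together.
- *That every PAID result reverses, including mediation.* The indirect effect does not, as shown in the working.
- *That Hypothesis 4 would misread a fall in distress under TC.* It uses baseline PAID only; the risk concerns which baseline group is said to benefit more.
- *That the harm can be sized in SD units.* The plan states no expected PAID effect.

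**Conclusion.** The point holds as a conflict between the stated PAID direction and the printed anchors, with no reverse-scoring described and no other supplied text to resolve it. The consequence is conditional: if ratings are scored in anchor order and labelled by the stated rule, Hypothesis 2 could report a true reduction in distress as a worsening. Hypothesis 4 could name the wrong baseline group, and Hypothesis 5 could carry reversed path signs and a reversed favorable-change label.

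The size is a complete reversal of sign or label for those quantities and nothing else. The indirect effect, two-sided p-values and the HbA1c and DSMP-SR group comparisons are untouched. The conclusion does not depend on whether items are coded 0-5 or 1-6, or on the simulated values. It rests on the ratings being ordered as printed and on no reversal being applied. If a reversal is applied, the stated direction is right and the defect shrinks to an unwritten scoring rule. The plan should be corrected, but this does not threaten the primary analysis.

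**What to change.** Before outcome data are analysed by arm, check the Teen and Parent instrument keys and rewrite the PAID entry in one of two ways, whichever the keys support:

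- items combined as printed, higher = more burden, lower = favorable; or
- items explicitly reverse-coded before they are combined, higher = less burden, higher = favorable.

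In either case, give the item values and the total-score formula for each form, and name the same favorable direction in Hypotheses 2, 4 and 5. The analysis code should apply that rule.

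Inferring the direction from the correlation of PAID with HbA1c is not a substitute. The plan states no expected correlation, and entry is limited to HbA1c 7.5-10.0%, so a weak or null result would settle nothing.

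The cost is one look at the keys, a few sentences of text and at most one line of code. No new data are needed, and sample size and power do not change.

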Experimental Design: Two TC teams (APN, RD and Psy. Fellow) will be constituted and trained, one each at NCH and AIDHC. A backup for each team member will also be identified and trained. Families will be randomized by [name] staff to TC-IP (n=50), TC-TH (n=50) or UC (n=50), using a prepared randomization list, stratified by insulin modality (pump or injections) and HbA_{1c} (\leq or $>$ 8.7%). We rejected randomization by sites due to logistical obstacles and since site differences might obscure detection of treatment effects. Randomization at the level of families reduces those concerns but introduces contamination issues as TC elements could intrude into UC visits. Efforts to counter this potential confound are described below. Each youth/parent will receive the assigned care (TC or UC) for approximately 4 successive follow-up visits across approximately 12 months. This period is adequate to detect clinically meaningful changes in HbA_{1c} and adherence. The design also permits exploratory analyses of modality of care (Face-to-Face vs. Telehealth), gender, race and ethnicity as moderators of treatment outcomes.

Treatment Conditions: The original RCT design is shown above. Treatment conditions include Usual Care and Transdisciplinary Care delivered in person or through telehealth. Elements of TC care are employed with some adolescents with T1D at AIDHC (i.e., APN and Psychologist see some patients together); this is much less true at NCH. AIDHC patients who have had such a visit within 12 months are ineligible for this study.

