Usual Care (UC) will include the multidisciplinary health care, education and supports that are routinely available to Nemours families of youth with T1D. This includes ~quarterly clinic visits with a pediatric endocrinologist or advanced practice nurse, with referrals to a certified diabetes educator, dietitian, social worker or psychologist as deemed clinically necessary by that HCP. T1D visit data will be extracted from Nemours EMR for each adolescent. Parental reports of care received elsewhere will be recorded. An EMR "Smart Form" used in several of [name] studies enables electronic capture of granular T1D visit data. Over 90% of Nemours T1D patients are on intensified regimens, i.e., insulin pump (~60%) or multiple daily insulin injections (~40%) using a "basal-bolus" approach and dietary carbohydrate counting. Treatment targets are HbA_{1c} $<$ 7.5% ($<$ 7.0% if deemed safe by attending MD) and minimization of symptomatic or severe hypoglycemia. A small, but growing, number of patients use continuous glucose monitors as part of their care.

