Prevention of TC-UC Contamination: Treatment integrity and internal validity of the RCT will be optimized by minimizing intrusion of TC elements into UC visits. We seek to prevent receipt of elements of the TC model of care during UC visits, including seeing multiple HCPs simultaneously, use of motivational interviewing or problem solving communication training methods during visits, receipt of behavioral and psychological interventions that are explicitly integrated with the patient's T1D care and education, and the intentional blurring of professional roles that are critical to the TC model. More TC teams would be ideal, but not affordable. Adolescents will be ineligible for the study if they have had one or more T1D clinic visits in the prior year that mimic TC (More than one health care provider seeing the adolescent concurrently) UC patients will continue to see their established HCPs. Thorough training of study clinicians about the need to segregate the TC and UC arms will further reduce contamination. A post-visit checklist completed by parents and a post-study questionnaire completed by HCPs providing care in the past year to study participants will assess the extent to which contamination occurs. Feedback to, or retraining of, project staff will be done if necessary. We will verify via EMR documentation any UC visits that include instances of multiple clinicians seeing the patient/family together. UC patients/families needing psychological services will be referred to psychologists who are not TC team members. We will document any psychological or psychiatric interventions received by UC patients outside of the study. It would be unethical for the researchers to constrain UC patients from receiving needed mental health interventions outside of the study.

Measurement Schedule and Protocol:

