Analytic Plans Primary endpoints are change in HbA_{1c} and DSMP-SR total score (treatment adherence) over 1 year. Secondary endpoints are: # of severe hypoglycemic events (Hypoglycemia Diary); measures of glycemic variability at each visit; and questionnaires obtained quarterly. The Full Analysis Set will include those who provide data at ≥ 1 follow-up visit. The Completer Analysis set will include those who provide data at all follow-ups. Efficacy analyses will be done on both sets.³¹³⁻³¹⁵ We will use multiple imputation for treatment of missing data.³¹³⁻³¹⁵ Obtained data will be summarized in graphs and tables. Categorical variables will be summarized by frequencies and percentages; continuous variables by mean, median, standard deviation (or SEM), minimum and maximum. Data will be summarized by primary group (UC and TC), secondary group (TC-TH, TC-IP, TC-IP/TH, TC-TH/CH) and measurement points.^{316,317} Model assumptions will be checked before analyses, and appropriate transformations or non-parametric methods will be used when indicated. For summarization of normally distributed data, group means and SEM will be presented. In case of substantial deviation from normality, boxplots will be presented. Exploratory subgroup analyses (e.g. race, ethnicity, gender, SES, secondary group) will be conducted as needed.^{318,319} Most tests will be performed against a two-sided alternative at the $\alpha = 0.05$ significance level and a 95% confidence interval and/or a p-value will be provided for inferential purposes. Data from both clinics will be pooled for analyses.^{316,317} All analyses will be done using the most recent version of SAS, SPSS, R or M-Plus.³¹⁵⁻³²² Demographic variables (age, gender, race, ethnicity, family structure, marital status, SES) and baseline values of primary and secondary end points, and questionnaire results will be summarized by group. If the normality assumption holds, t-tests of continuous baseline variables and Fisher exact test/chi-square test/CMH test for categorical variables will be used to compare the TC and UC groups at baseline; one-way ANOVA will be used for comparisons of secondary groups. The statistician will select analytic methods based on data distributions and any imbalanced baseline scores.³²³ Linear mixed effects modeling (continuous outcomes) or generalized linear mixed modeling (categorical outcomes) is planned for the hypotheses below.³¹⁵⁻³²² Treatment group (UC vs TC) and demographic characteristics will be fixed effects in these models, while site, physician, and within-subject effects will be random effects. The same analyses will be attempted for secondary groups, sample size permitting. We will use Holmbeck's methods³²⁴ to evaluate baseline demographic variables and questionnaire scores as moderators of TC-UC effects on primary outcomes and to evaluate mediation of effects on primary endpoints. Candidate mediators are variables that are obtained serially concurrent with the primary endpoints at ≥ 3 visits.

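### Two clinics are pooled with site as a two-level random effect and no TC-UC estimate by site, so a large site or team difference in the TC effect would go unseen

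*Combined protocol and SAP*

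**What the plan says.** All references are to section 3.4 of the combined protocol and SAP.

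- **Analytic Plans.** "Data from both clinics will be pooled for analyses". Treatment group and demographic characteristics are fixed effects, "while site, physician, and within-subject effects will be random effects". No treatment-by-site term is stated. The planned moderators are demographic variables and questionnaire scores. The exploratory subgroups are given as examples, and neither site nor team is among them.
- **Experimental Design.** "Two TC teams (APN, RD and Psy. Fellow) will be constituted and trained, one each at NCH and AIDHC". Also: "A backup for each team member will also be identified and trained". Randomization is by family, stratified by insulin modality and HbA1c but not by site. Site differences are cited there, and again under Limitations, as a reason not to randomize whole sites.
- **Treatment Conditions.** "Elements of TC care are employed with some adolescents with T1D at AIDHC"; the same sentence says this is much less so at NCH. AIDHC patients with such a visit in the previous 12 months are excluded.
- **Prevention of TC-UC Contamination, Diabetes Care Inventory (DCI) and Hypothesis 3.** Parents complete a checklist after visits, joint UC visits are verified in the EMR, and providers complete the DCI for each participant. Hypothesis 3 compares DCI scores between TC and UC. None of this is planned by site.

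**The concern.** Two features could make the TC effect differ between the clinics. Background care is closer to TC at one of them, and each clinic's TC arm is delivered by a single team. The only provision for site in the model is a random effect with two levels. A variance based on two units has one degree of freedom, so the data say almost nothing about its size. The plan does not say whether the random effect is an intercept or also a slope. An intercept does not let the TC effect vary by site, and a slope would be no better identified with two sites.

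The trial is meant to guide a larger multi-site RCT. For that purpose, a TC effect seen with both teams and one that comes from a single team lead to different designs. The planned output would not show which had occurred.

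**Working it through.** **The plan's own figure.** The plan gives no figure about site. The nearest is the power for a 0.5% HbA1c difference with 65 TC and 35 UC: 87.4%, 71.3% and 50.9% at SD 0.7, 1.0 and 1.5. A two-sided t test at 0.05 gives 92.1%, 65.6% and 35.0%. The mismatch is a separate matter, and nothing below depends on it.

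**Inputs.**
- From Sample Size and Statistical Power: N = 100 (65 TC, 35 UC); effect 0.5%; SD 0.7% (alternative 1.0%); DSMP-SR difference 7.0 points, about 0.6 SD, so SD ≈ 7.0/0.6 = 11.7.
- Assumed, because the documents do not give them: 50 analysed patients per site (the original target was about 75 of 150 at each) and the 65:35 ratio within each site. The cells are then 32.5 TC and 17.5 UC per site.

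**Step 1. Information on a two-site variance.** With 1 df, the 95% limits for an SD run from √(1/5.024) = 0.45 to √(1/0.000982) ≈ 32 times the estimate.

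**Step 2. What pooling shows.** With equal sites and true benefits of 1.0% and 0%, the expected pooled effect is 0.5 × 1.0 + 0.5 × 0 = 0.5%, the same as for a uniform 0.5%. A simulation of a random-site-intercept model (300 runs per scenario, one outcome per patient, SD 0.7, assumed site shift 0.3) gave:

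| True TC benefit | Mean pooled estimate | Runs significant |
|---|---|---|
| 1.0% and 0% | 0.50 | 90% |
| 0.5% at both | 0.48 | 91% |

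A treatment-by-site test flagged the first case in 95% of runs; the noncentral-t calculation gives 92%. Some mixed-model fits gave boundary or convergence warnings, as expected with two levels.

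**Step 3. Precision of by-site estimates** (residual variance pooled over the four cells, 96 df, t = 1.985).
- Per site: SE = 0.7 × √(1/32.5 + 1/17.5) = 0.7 × 0.2965 = 0.208; half-width 1.985 × 0.208 = 0.41%.
- Between-site difference: SE = √2 × 0.208 = 0.29; half-width 0.58%.
- DSMP-SR: per-site SE = 11.67 × 0.2965 = 3.46, half-width 6.9 points; between-site SE 4.89, half-width 9.7 points.

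**Step 4. Power for a between-site difference in the HbA1c effect.**

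| Scenario | 0.5-point difference | 1.0-point difference | Detectable at 80% power |
|---|---|---|---|
| 50/50 split, SD 0.7 | 39% | 92% | 0.83 |
| 70/30 split, SD 0.7 | 34% | 87% | 0.91 |
| 50/50 split, SD 1.0 | 22% | 66% | 1.19 |

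These figures treat 12-month HbA1c as a single outcome. Adjusting for baseline or using repeated measures could narrow the intervals.

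**The case against.** The strongest reply is that the site difference in UC is already managed. Recent joint-visit patients are excluded, UC families stay with their established providers, and contamination is measured in three ways and compared between arms through the DCI. This largely stands: these measures reduce the difference and give real information on contamination. But the exclusion acts only before enrolment, and none of the measures is linked to site or to the treatment effect.

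It is also fair that a by-site look is unplanned rather than ruled out, since the subgroup list is open-ended, and that the supportive analysis is weak. As an illustration with no source in the documents, suppose 20% to 40% of AIDHC UC families had joint visits carrying half to all of the TC benefit. The site effects would differ by 0.5 × 0.2 × 0.5 = 0.05% to 0.5 × 0.4 × 1 = 0.20%. With SE 0.29, power is about 5% to 10%. Modest contamination would therefore not be seen.

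Three stronger readings are tempting but not supported:

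- **The definition of UC contradicts itself.** A reader might set "Usual Care (UC) will include the multidisciplinary health care, education and supports that are routinely available to Nemours families" against "We seek to prevent receipt of elements of the TC model of care during UC visits" and conclude that AIDHC's joint visits are both part of UC and barred from it. The UC paragraph goes on to describe visits with an endocrinologist or an advanced practice nurse, with referral to other disciplines. Table 2 likewise places the psychologist on referral, usually on another day. Read together, UC is single-provider care with referral.
- **Pooling biases the TC effect.** It does not. Families are randomized individually at both clinics.
- **A site variance estimated at zero damages the analysis.** Even with a true 0.2% site difference and equal sites, omitting site raises the residual SD only from 0.70 to √(0.49 + 0.01) = 0.707.

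**Conclusion.** The point holds as a limited one. A two-level random effect for site is a poor choice, and without any by-site estimate a large difference in TC effect between sites or teams would be hidden: 1.0% and 0% cannot be told from 0.5% at both. The pooled contrast remains a valid average over these two sites, so the weakness lies in hidden heterogeneity and in what can be carried to a larger trial, not in bias. The remedy can reveal only large divergences, roughly 0.8% HbA1c or more with 80% power if the SD is 0.7% and the sites are equal in size, and larger ones otherwise. No analysis can say whether a divergence comes from the team or from the site. The sizes rest on the assumed site split, a 65:35 ratio within sites and the plan's SDs.

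**What to change.** In the Analytic Plans of section 3.4:

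1. Fit site as a fixed effect.
2. Pre-specify, for HbA1c and DSMP-SR, the TC-UC difference by site with 95% confidence intervals and a treatment-by-site contrast, labelled descriptive and supportive.
3. Beside these estimates, tabulate by site and arm the DCI scores, and by site the share of UC visits with joint providers from the EMR check already planned.
4. State that team and site cannot be separated.

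The cost is SAP wording, one supportive model per primary endpoint and a short table, with no new data. The drawback is imprecision: a by-site result compatible with no difference must not be read as evidence that the sites agree.
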